## 15.7 Sample Size and Randomization

This study will enroll 55 participants, who will be evaluated for the course of 14 weeks, including screening. Power analysis for this pilot study indicates that a minimum of 135 person-observations will be sufficient to test whether MA use or the psychosocial Addiction Severity Index (ASI) are associated with CTRA gene expression, assuming a medium effect size of 0.15 and power level of .80. Additionally, a logistic model testing whether CTRA is associated with viral suppression would require a minimum of 154 person-observations, assuming a power level of .80, a CTRA standard deviation of 1.44, mean centering of CTRA, and an odds ratio of 1.5. When modeling viral load as a continuous outcome, 135 person-observations is the minimum to test whether CTRA is associated with viral load (c/mL), assuming a medium effect size of 0.15 and power level of .80. These analyses will include 55 participants over four measurements of CTRA, for a total of 220 person-observations (176 person-observations at 80% retention), which is sufficient for these thresholds.

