Primary Analysis Plan	Using a linear mixed effects regression, we will test whether a negative MA urine test is associated with reductions in CTRA contrast scores across four time points—Visits B, 4.2 (Week 4), 8.2 (Week 8), and 12.0 (Week 12 follow-up). We will use a time (days) by MA urine result interaction term to estimate difference in change in CTRA as a function of MA test result. Using a mixed effects logistic regression, we will test whether CTRA expression is associated with viral suppression (<200c/mL) across three time points— Visits B, 4.2 (Week 4), 8.2 (Week 8), and 12.0 (Week 12 follow-up). We will include a time (days) by CTRA expression interaction term to test this association longitudinally.
Rationale for Number of Subjects	Power analysis for this pilot study indicates that a minimum of 135 person-observations will be sufficient to test whether MA use or the psychosocial Short Inventory of Problems (SIP-R) are associated with CTRA expression, assuming a medium effect size of 0.15 and power level of .80. Additionally, a logistic model testing whether CTRA is associated with viral suppression would require a minimum of 154 person-observations, assuming a power level of .80, a CTRA standard deviation of 1.44, mean centering of CTRA, and an odds ratio of 1.5. When modeling viral load as a continuous outcome, 135 person-observations is the minimum to test whether CTRA is associated with viral load (c/mL), assuming a medium effect size of 0.15 and power level of .80. These analyses will include 55 participants over four measurements of CTRA, for a total of 220 person-observations (176 person-observations at 80% retention), which is sufficient for these thresholds.

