**10.2 Baseline (Visit B, one week before Visit 1.1)**

1. Urine drug test
2. Behavioral survey
3. Blood draws (~50 mL total) for:
  - a. PBMCs for transcriptome profiling (~34 mL)
  - b. HIV viral load (~6 mL)
  - c. COVID-19 immunoassay (~8.5 mL)
4. HIV medications review
5. Measure weight and height
6. Record any adverse events

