### 15.6 Multivariate Analysis for Associations Between Endpoints

Associations between MA use, CTRA gene expression, and viral suppression. All models in Aim 1 will adjust for age, race, education, employment, housing, and mRNA encoding markers of major leukocyte subsets (e.g., CD4). We will also assess for confounding by COVID-19 infection detected by immunoassay, liver function, and type of ART prescription. MA use and CTRA. Using a linear mixed effects regression, we will test whether a negative MA urine test is associated with reductions in CTRA contrast scores across four time points—Visits B, 4.2, 8.2, and 12.0. We will use a time (days) by MA urine result interaction term to estimate difference in change in CTRA as

a function of MA test result. CTRA and viral load. Using a mixed effects logistic regression, we will test whether CTRA gene expression is associated with viral suppression (<200c/mL) across three time points—Visits B, 4.2, 8.2, and 12.0. We will include a time (days) by CTRA gene expression interaction term to test this association longitudinally. We will also test whether CTRA and viral load are reciprocally associated using dynamic panel data modeling with maximum likelihood (102-104). This approach will allow us to simultaneously test whether CTRA is associated with viral load at subsequent observations, and account for whether CTRA is affected by prior values of viral load (102-104).

**Associations between psychosocial indicators of substance use severity and CTRA.** Using a linear mixed effects regression, I will test whether the seven domains of the Addiction Severity Index (ASI) is associated with reductions in CTRA contrast scores across four time points—Visits B, 4.2, 8.2, and 12.0. I will use a time (days) by ASI domain score interaction term to estimate change in CTRA as a function of changes in ASI scoring. We will control for age, race, education, and mRNA markers of major leukocyte subsets.

**Indirect associations between MA use, CTRA, and viral suppression.** I will use propensity scores to test the degree to which CTRA mediates the association between MA use and viral suppression (105, 106). The general theory is that we would compute propensity score for CTRA—the probability of having a particular CTRA level—to compare participants who used MA with those who would have had the same value of the CTRA had they used MA.

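### The 154 observations for the viral-suppression model size one CTRA coefficient; they do not support 80% power for the planned time-by-CTRA test

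*Combined protocol and SAP*

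**What the plan says.** Section 15.7 states that "a logistic model testing whether CTRA is associated with viral suppression would require a minimum of 154 person-observations". The synopsis repeats the figure, "assuming a power level of .80, a CTRA standard deviation of 1.44, mean centering of CTRA, and an odds ratio of 1.5". Neither place gives an alpha, sidedness, suppression probability, covariate R-squared or interaction effect. Section 15.7 then concludes that the design yields "a total of 220 person-observations (176 person-observations at 80% retention), which is sufficient for these thresholds".

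The analysis is set out in section 15.6: "Using a mixed effects logistic regression, we will test whether CTRA gene expression is associated with viral suppression (<200c/mL"). The next sentence adds: "We will include a time (days) by CTRA gene expression interaction term to test this association longitudinally". The synopsis, under Primary Analysis Plan, says the same: "We will include a time (days) by CTRA expression interaction term to test this association longitudinally". On covariates, section 15.6 says: "All models in Aim 1 will adjust for age, race, education, employment, housing, and mRNA encoding markers of major leukocyte subsets". CTRA is described as mean-centred. Nothing is said about the origin or centring of time.

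**The concern.** One odds ratio for CTRA can size a test of whether CTRA is related to suppression. It cannot size a test of whether that odds ratio changes over time, which is what a time-by-CTRA term measures. The effect the plan assumes, read as a constant odds ratio of 1.5, is a case in which the interaction is exactly zero.

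Adding the interaction also changes the meaning of the remaining CTRA coefficient: it becomes the CTRA effect at time zero. Mean-centring CTRA does not alter this, because it only changes the meaning of the time coefficient. What matters is where time is zero.

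The link between CTRA and viral load is part of the primary objective in section 3.1, and this model is in the synopsis's primary analysis plan. If the interaction is read as the test, a null result would be the expected outcome even when CTRA is related to suppression just as assumed, and it could be reported as no association.

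**Working it through.** **Inputs from the documents.** Power 0.80, CTRA SD 1.44, odds ratio 1.5 (read as per CTRA unit), 154 required, 220 planned and 176 at 80% retention. There are four measurements: Baseline and Weeks 4, 8 and 12. Section 10.2 puts Baseline a week ahead of the first treatment visit, so both 0/4/8/12 and 0/5/9/13 weeks are tried.

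**Assumed, because not stated.** Two-sided 5% level; rows independent, as the plan's person-observation count implies; and, for the interaction, an odds ratio moving from 1.0 to 1.5 across follow-up.

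**Reproducing 154.** The Hsieh formula for one normal predictor is N = (1.960 + 0.842)² / [p(1−p)(ln 1.5 × 1.44)²] = 7.849 / [p(1−p) × 0.3409].
- p = 0.817: 153.99, so 154. At p = 0.5 it gives 93, and at p = 0.9 it gives 256.
- p = 0.5 with a covariate R² of 0.40: 92.1 / 0.60 = 153.5, so 154.
- The Demidenko formula at p = 0.5 gives 115.2; with R² = 0.25, 115.2 / 0.75 = 153.6, so 154.

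The stated inputs therefore do not fix N. Every completion found that reaches about 154 sizes one CTRA coefficient without an interaction. The next three steps scale from the 154 itself, so they do not depend on which completion was used.

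**Average CTRA effect (no interaction, or time centred).** λ(N) = 2.802 × √(N/154), which is 2.995 at 176 and 3.349 at 220. Power = Φ(λ − 1.960) = 85% and 92%.

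**CTRA coefficient with time counted from Baseline.** Its variance is multiplied by 1 + t̄²/var(t).
- Weeks 0/4/8/12: 1 + 36/20 = 2.80. λ = 1.790 and 2.001; power 43% and 52%.
- Weeks 0/5/9/13: 1 + 45.56/23.19 = 2.96. λ = 1.739 and 1.945; power 41% and 49%.
- For 80% power: 154 × 2.80 = 431 to 154 × 2.965 = 457 observations.

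**Interaction.**
- Constant odds ratio of 1.5: the null is true, so rejection is about 5% at any N.
- Odds ratio rising from 1.0 to 1.5: λ is multiplied by √(var(t)/T²), where T is the length of follow-up. For 0/4/8/12, var(t)/T² = 20/144 = 0.139, so λ = 1.116 and 1.248, and power is 20% at 176 and 24% at 220. For 0/5/9/13 the ratio is 0.137 and the rounded powers are the same. For 80% power: 154 × 7.2 = 1,109 to 154 × 7.29, or about 1,120, observations.

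**If suppression is near 50% with no covariate allowance.** The interaction has λ = √(N × 0.25 × 0.3409 × 0.139) = 1.44 and 1.61, giving 30% and 36%; simulation gives 27% and 32%. The CTRA coefficient with time from Baseline has simulated power of 53% and 64%.

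**Simulation check (3,000 datasets per setting, 82% suppression, 176 and 220 rows).**

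| Test | 176 | 220 |
|---|---|---|
| CTRA, time centred, constant OR 1.5 | 83% | 91% |
| CTRA, time from Baseline, constant OR 1.5 | 37% | 45% |
| Interaction, constant OR 1.5 | 5% | 5% |
| Interaction, OR 1.0 to 1.5 | 19% | 23% |

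**The case against.** The strongest reply is that the plan does not rest the conclusion on the interaction alone. Section 15.6 first says the model tests whether CTRA is associated with suppression, which matches the wording of section 15.7, and only then adds the interaction. A joint two-degree-of-freedom test of both CTRA terms does not depend on how time is coded. Under a constant odds ratio of 1.5 its noncentrality is λ² = 8.97 and 11.21, giving about 77% power at 176 and 86% at 220. That is a fair reading, but the plan does not specify such a test, and it too falls short of 80% at the plan's own retention figure. The gap that stands is that no coefficient is named as the test.

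A second reply is that the interaction figures rest on a path the documents do not give. That is so. But for the interaction to need only 154 observations, the odds ratio would have to change by a factor of 1.5 per SD of time, which is exp(0.405/0.373), or about threefold, over follow-up. No such effect appears in the plan.

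Two stronger readings are tempting. A reader might infer that neither CTRA coefficient has 80% power. The documents do not support that: they are silent on the origin of time, and with time centred the CTRA coefficient keeps about 85% at 176. A reader might also infer that 154 must come from a single-predictor formula at about 82% suppression. That is one back-calculation among several, and some of the others include a covariate allowance.

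Finally, this is a pilot, and section 15 promises a detailed SAP before the final analysis. That leaves room to settle the point, but it does not make the sufficiency statement correct as written.

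**Conclusion.** The concern holds in this form: the 154, and the statement that 176 to 220 observations suffice, apply to one CTRA coefficient and not to the time-by-CTRA term. The interaction's rejection rate is about 5% under the plan's own constant effect. Under the assumed rise from 1.0 to 1.5 it is about 20-24%, or roughly 27-36% if suppression is near 50%. The power of the lower-order CTRA coefficient is undetermined until the origin of time is stated; the choice roughly halves it at 176 observations, from 85% to 41-43%.

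These figures rest on a two-sided 5% level, independent rows and visits on schedule. Within-person correlation and the planned covariates would change them. The mismatch between the sized effect and the interaction does not depend on those assumptions.

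**What to change.** In section 15.6 and the synopsis, centre time at the mean visit day, or fit the model without the interaction. Name the average CTRA coefficient over the four visits as the test that the 154 supports, and report time by CTRA as a secondary term.

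In section 15.7 and the synopsis, limit the 154 and the sufficiency statement to that coefficient. State the alpha, sidedness, suppression probability and covariate R² that the sponsor actually used; 82% should not be written in as though it were the sponsor's input. Either give the interaction its own assumed effect and power, or say that it is not powered.

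The cost is a few sentences, with no new data or participants. The small downside is a less favourable stated power for the interaction.

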### 3 STUDY OBJECTIVES

#### 3.1 Primary Objective

To investigate whether changes in CTRA gene expression coincide with changes in MA use and viral load over the course of 12 weeks in HIV-positive MSM with and without MUD.

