#### HIV-positive MSM non-substance-using control (N = 20)

1. Identifies as (cis- or transgender) female
2. Positive test for MA, opioids, cocaine, and/or MDMA.
3. Reports substance use (MA, opioids, cocaine, MDMA, hallucinogens, heavy alcohol use, and/or tobacco) in the past 6 months
4. Reports past or current substance use disorder

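### The 220-row count (176 at 80% retention) does not show sufficiency for the within-person MA-use and SIP-R/ASI associations: the CM arm supplies 140 rows, or 112 at 80% retention, against a stated minimum of 135

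*Combined protocol and SAP*

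**What the plan says.** Section 15.7 gives the threshold for the exposure tests: "a minimum of 135 person-observations will be sufficient to test whether MA use or the psychosocial Addiction Severity Index (ASI) are associated" with CTRA. The effect size is 0.15, described as medium, and the power is 0.80. The synopsis gives the same 135 but names a different instrument: "whether MA use or the psychosocial Short Inventory of Problems (SIP-R) are associated with CTRA expression". Neither place states alpha, the number of predictors or a within-person correlation.

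Both places set one row count against every threshold. Section 15.7: "These analyses will include 55 participants over four measurements of CTRA, for a total of 220 person-observations". Synopsis: "for a total of 220 person-observations (176 person-observations at 80% retention), which is sufficient for these thresholds".

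The 55 participants are 35 in the CM arm and 20 controls. Section 6.3 excludes a control for "Positive test for MA, opioids, cocaine, and/or MDMA", for reported use of listed substances in the past 6 months, and for "Reports past or current substance use disorder". Section 8.2 has controls give urine and complete surveys at all four CTRA visits.

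The synopsis describes the design as within-subjects. Objective 3.1 asks "whether changes in CTRA gene expression coincide with changes in MA use and viral load", in men with and without MUD. Section 15.6 tests this with a linear mixed regression of CTRA on urine result and a time-by-urine-result term. It states no arm term, no arm-by-time term and no restriction to the CM arm.

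**The concern.** Whether CTRA changes when a person's MA use changes can be learned only from people whose MA use changes. Controls are chosen to be MA-negative, so their urine result is expected to be the same at all four visits and their drug-problem score to stay low. They supply a reference level for CTRA, which is the role section 4.1 gives them, but little or nothing on the within-person exposure contrast. Counting their 80 rows toward the 135 makes the margin for that question look wider than it is.

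If the statement stays, a null MA–CTRA or SIP-R/ASI–CTRA result will be read as coming from a test that met the plan's own size requirement, when at the planned retention the arm that carries the exposure change does not meet it.

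**Working it through.** **Inputs.** From the documents: 35 CM and 20 control participants, four CTRA visits, 80% retention, minimum 135 rows, effect size 0.15, power 0.80. Assumed because not stated: alpha 0.05, 0.15 read as Cohen's f², ICC from 0 to 0.7, the CM urine patterns below, and the same 80% retention in both arms.

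**1. The plan's count.** 55 × 4 = 220 and 220 × 0.80 = 176. Both are correct, and both exceed 135.

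**2. The count by arm.**

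| | Full retention | 80% retention |
|---|---|---|
| CM | 35 × 4 = 140 | 140 × 0.80 = 112 |
| Control | 20 × 4 = 80 | 80 × 0.80 = 64 |
| Total | 220 | 176 |

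The CM arm is 140 − 135 = 5 rows above the minimum at full retention and 135 − 112 = 23 below it at 80% (112/135 = 83%). The retention at which the CM arm just reaches 135 is 135/140 = 96.4%.

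**3. Where 135 may come from.** With a noncentral F test and noncentrality f² × N, the omnibus test of all predictors needs 131 rows for 13 predictors, 135 for 14 (power 0.802) and 139 for 15. The plan's figure is therefore reproduced by a 14-predictor omnibus test, but that is an inference. Other readings do not give 135: one coefficient needs 55–56 rows, a 7-df test 103–104, and 0.15 read as a correlation 347.

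**4. What control rows add.** Take a random-intercept model with V = (1 − ICC)·I + ICC·J over the four visits. The variance of a coefficient is its diagonal element of (ΣX′V⁻¹X)⁻¹. The table gives that variance for 35 CM plus 20 always-negative controls, divided by the variance for 35 CM alone. The CM urine pattern is assumed: 10% negative at baseline and about 55% later. The main-effect rows are from a model without the interaction.

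| Coefficient and extra terms | ICC 0 | ICC 0.3 | ICC 0.5 | ICC 0.7 |
|---|---|---|---|---|
| MA main effect, no arm terms | 0.637 | 0.762 | 0.823 | 0.872 |
| MA main effect, arm added | 0.957 | 0.944 | 0.939 | 0.936 |
| Time-by-MA, no arm terms | 0.511 | 0.497 | 0.492 | 0.489 |
| Time-by-MA, arm added | 0.519 | 0.499 | 0.493 | 0.490 |
| Either, arm and arm-by-time added | 1.00 | 1.00 | 1.00 | 1.00 |

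Dividing 112 by the unrounded ratio gives CM-equivalent rows at 80% retention:
- Main effect, no arm terms: 176, 147, 136 and 128.
- Main effect, arm added: 117 to 120.
- Time-by-MA, no arm terms: 219 to 229.
- Either coefficient, both arm terms added: 112.

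A second assumed pattern (CM MA-positive rates 0.90, 0.50, 0.45, 0.55) gives 0.62–0.91 for the main effect and 0.43–0.48 for time-by-MA without arm terms. It also gives 1.00 with both terms.

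**5. What that gain rests on.** Under the second pattern, suppose the arms differ by 1 unit of CTRA for reasons other than current MA use. Without an arm term the MA main effect then moves by 0.61 (ICC 0), 0.33 (0.3), 0.21 (0.5) or 0.11 (0.7). With an arm term it moves by zero. The time-by-MA gain survives an arm term but vanishes with arm-by-time, so it rests on controls and urine-negative CM participants having the same time slope.

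Steps 4 and 5 concern the urine exposure only. The plan gives no distribution for SIP-R or ASI scores, so no parallel figure is offered for them.

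**The case against.** The strongest reply is that the plan's model is pooled. Section 15.6 has no arm terms, controls are tested and surveyed at every CTRA visit, and objective 3.1 covers men with and without MUD. In that model always-negative controls are part of the exposure contrast and help fix the time slope of negative rows; the variance of the time-by-MA term roughly halves. This stands. A reader might infer that only CM rows bear on the MA test, or that 220 is an arithmetic error. The documents support neither.

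Three further stronger readings also go too far.
- **Controls cannot vary.** The exclusions apply at entry, later urine is tested, and cannabis and non-heavy alcohol are not on the list of excluded substances. The most that can be said is that controls are expected not to vary in MA use and to score low on drug problems.
- **Sufficiency fails outright.** At full retention 140 exceeds 135, and section 12.4 replaces those who withdraw before Visit 5.2, which may recover rows. Section 15.7 does not, however, rely on replacement in its count.
- **Power of the MA test is 69%.** That is the power of the inferred 14-predictor omnibus test at 112 rows. An omnibus test is not a test of MA use, and control rows inform it through the covariates. If f² = 0.15 belonged to the MA coefficient alone and rows were independent, 112 rows would give 98%.

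What the reply does not rescue is the step from the pooled count to the within-person question. The main-effect gain comes from a contrast confounded with MUD status, and the interaction gain from a shared trend that the plan does not state as an assumption.

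**Conclusion.** The point holds for the within-person association. For the MA-use and SIP-R/ASI tests under objective 3.1, the CM arm supplies 140 rows, which meets 135, or 112 at the plan's own 80% retention, which is 23 short. CM retention of at least 96.4% would be needed, before any replacement. Control rows add precision to the pooled model of 15.6, but none once arm and arm-by-time are fitted.

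The row counts follow from the documents, given equal retention in both arms. The variance ratios rest on assumed ICCs and urine patterns. The true power for the MA coefficient cannot be settled from the plan, because alpha, the predictor count, the ICC and the basis of 135 are all unstated. Rows from the same person are also not independent, so 112 against 135 is a check on the plan's own terms and not an effective sample size.

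**What to change.** In 15.7 and the synopsis, stop claiming that 220/176 rows are sufficient for the within-person MA-use and SIP-R/ASI associations. Report 140 CM rows (112 at 80% retention) for these tests and say that 112 is below 135. Give power or detectable effect for the MA or time-by-MA coefficient, based on 35 CM participants, a stated alpha and a range of ICCs.

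Make 15.6 agree: either add arm and arm-by-time terms to the MA and SIP-R/ASI models, or label the estimate as pooled and state the assumption that controls and urine-negative CM participants share the same CTRA level and trend. Keep 220/176 as the row count for the CTRA–viral suppression and CTRA–viral load tests, where control CTRA does vary. Use one instrument name throughout, since the synopsis says SIP-R and 15.6 and 15.7 say ASI.

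The cost is one paragraph reworded in two places, a model statement in 15.6 and a short power calculation. No participants are added. The downside is that the stated figure becomes less favourable.

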### **12.4 Replacement of Subjects**

Subjects who withdraw from the study before Visit 5.2 will be replaced.

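### Section 15.7 counts repeated-visit rows as if they were independent, so its sufficiency claim does not establish 80% power for the mixed viral-suppression model

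*Combined protocol and SAP*

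**What the plan says.** Section 15.7 and the synopsis (Rationale for Number of Subjects) give two minima in person-observations.

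- Linear models: "a minimum of 135 person-observations will be sufficient to test whether MA use" or psychosocial problems are associated with CTRA, at an effect size of 0.15 and power 0.80. The same 135 is given for continuous viral load.
- Logistic model for viral suppression: 154, "assuming a power level of .80, a CTRA standard deviation of 1.44, mean centering of CTRA, and an odds ratio of 1.5".

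The supply side follows, with each of the 55 people contributing four CTRA visits: "for a total of 220 person-observations (176 person-observations at 80% retention), which is sufficient for these thresholds".

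The analysis is specified elsewhere. Section 15.6 states: "Using a mixed effects logistic regression, we will test whether CTRA gene expression is associated with viral suppression", with a time-by-CTRA interaction. The synopsis puts the same model in its Primary Analysis Plan. Section 15.6 adds: "All models in Aim 1 will adjust for age, race, education, employment, housing, and mRNA encoding markers of major leukocyte subsets". On attrition, section 12.4 says: "Subjects who withdraw from the study before Visit 5.2 will be replaced".

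**The concern.** Four visits from one person carry less information about a between-person association than single visits from four people. A row count can be set against a minimum only if that minimum already allows for within-person correlation. The listed assumptions contain no ICC, random-effect variance or design effect. They also omit alpha, the suppression rate, and whether the odds ratio is subject-specific (what a mixed logistic model estimates) or marginal.

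This sentence is the stated justification for 55 participants. Without the missing inputs, a reader of a null CTRA–suppression result cannot tell whether the test had about 50% or about 90% power.

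**Working it through.** **1. The row count.** 55 × 4 = 220 and 220 × 0.80 = 176. Both reproduce. The margins over the logistic minimum are 176/154 = 1.14 and 220/154 = 1.43.

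**2. Where 135 may come from.** Take the overall F test in ordinary regression with f² = 0.15, alpha 0.05 (assumed) and noncentrality f² × N. The smallest N for 80% power is 131 with 13 predictors, **135 with 14** (power 0.802) and 139 with 15. An exact match to an independent-row calculation therefore exists.

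**3. Where 154 may come from.** The independent-row formula for one continuous covariate, with two-sided alpha 0.05 assumed, is

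N = (1.96 + 0.8416)² / [p(1−p) × (ln 1.5 × 1.44)²] = 23.02 / [p(1−p)].

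| Suppression rate p | 50% | 70% | 80% | 81.7% | 85% | 90% |
|---|---|---|---|---|---|---|
| Rows needed | 93 | 110 | 144 | 154 | 181 | 256 |

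The stated 154 appears at p = 81.7% (or 18.3%). Since p is free, this match proves little alone, but it shows that 154 cannot be reproduced from the stated inputs.

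**4. How much correlation the margin absorbs.** Approximate the design effect as 1 + 3c, where c is the product of the within-person correlations of CTRA and of suppression. If 154 is an independent-row figure, 176 rows meet it only when c ≤ (176/154 − 1)/3 = 0.048, and 220 rows only when c ≤ (220/154 − 1)/3 = 0.143.

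**5. Power under the planned type of model.** Random-intercept logistic simulation of the CTRA main effect:

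- 55 people, CTRA SD 1.44, no covariates.
- Random-intercept SD 1.0 or 1.5 (latent outcome ICC 0.23 or 0.41); CTRA ICC 0.3 or 0.7. All of these are assumptions.
- Likelihood-ratio test at 0.05; 2,000 runs per cell (Monte Carlo SE about 1 point); null rejection 5.5%.
- 176 rows: a random 176 of the 220 visits. 198 rows: 44 × 4 + 11 × 2, which assumes early withdrawals are replaced and 11 people are lost after Visit 5.2.

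Power at 81.7% suppression:

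| Outcome ICC / CTRA ICC | Subject-specific OR 1.5: 176 / 198 / 220 rows | Marginal OR 1.5: 176 / 198 / 220 rows |
|---|---|---|
| 0.23 / 0.3 | 0.685 / 0.733 / 0.782 | 0.803 / 0.850 / 0.885 |
| 0.23 / 0.7 | 0.637 / 0.671 / 0.725 | 0.734 / 0.781 / 0.794 |
| 0.41 / 0.3 | 0.599 / 0.627 / 0.686 | 0.790 / 0.856 / 0.882 |
| 0.41 / 0.7 | 0.509 / 0.545 / 0.575 | 0.710 / 0.754 / 0.787 |

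Without clustering the same simulation gives 79–83% at 176 rows and 88% at 220. At this rate a subject-specific OR of 1.5 corresponds to a marginal OR of 1.42 (ICC 0.23) or 1.36 (ICC 0.41).

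Power at other suppression rates, 176 / 220 rows:

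| Rate | Subject-specific | Marginal |
|---|---|---|
| 50% | 64–86% / 74–93% | 89–96% / 95–99% |
| 70% | 60–81% / 67–87% | 84–92% / 89–97% |
| 90% | 38–51% / 44–59% | 52–60% / 60–70% |

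A second simulation (600 runs per cell, 176 rows as 44 complete participants, subject-specific OR, 81.7% suppression) was below 80% in every cell with outcome ICC 0.3 or more, at both row counts.

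**6. The linear models.** If 0.15 is the tested term's own partial f², 55 independent rows suffice. If 0.15 is the whole-model f², 135 covers all predictors jointly and says nothing about the time-by-urine coefficient; 176 independent rows then give 80% for one term only when its partial f² is about 0.045 or more. No shortfall is shown here. No power is stated for time-by-CTRA either.

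**The case against.** No sum in section 15.7 is wrong: 220 and 176 do exceed 135 and 154. The independent-row origin is also unproven. At alpha 0.01, 135 fits six predictors equally well. Multiplying the logistic formula by a design effect of 1.15, 1.30 or 1.60 also returns 154, at suppression rates of about 78%, 74% and 60%. With a marginal OR at 50% or 70% suppression, every simulated cell exceeds 80%, even at 176 rows. The ICCs are not taken from the documents. Part of the loss at 81.7% comes from reading the odds ratio as subject-specific: comparing paired cells at 176 rows, that reading costs 10 to 20 points. Finally, this is a pilot, viral load is a listed secondary endpoint, and section 15 promises a detailed SAP.

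Most of this stands as a limit on the conclusion: underpowering is not demonstrated, and the derivation of the minima is inference. It does not rescue the claim. If a design effect was included, it is not among the listed assumptions. The two odds ratios differ only because people differ from one another, so that ambiguity is part of the same omission. A pilot need not claim 80% power, but this one does, and the synopsis lists the suppression model in its Primary Analysis Plan. A future SAP does not support a sufficiency statement made now.

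**Conclusion.** The concern holds. Comparing 220 or 176 correlated rows with 154 does not show 80% power for the mixed suppression model. Depending on inputs the plan omits, power at 81.7% suppression runs from 51% (176 rows, subject-specific OR) to 89% (220 rows, marginal OR). It is generally higher at lower suppression rates and is 38–70% at a rate of 90%. These figures rest on assumed ICCs, suppression rates and loss patterns, and omit the covariates and the time-by-CTRA term. The study is not shown to be underpowered under every reading, and no deficit is shown for the linear models. This should be fixed, but it does not call the design into question.

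**What to change.** Keep N=55. In section 15.7 and the synopsis, replace the sufficiency sentence with power, or the detectable effect, for the planned mixed models: the CTRA main effect, time-by-CTRA and time-by-urine.

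- Allow for within-person correlation and for the replacement of early withdrawals, over stated ranges of ICC and suppression rate (for example 50–90%).
- State alpha, whether the OR of 1.5 is subject-specific or marginal, and whether 0.15 is a partial or whole-model f².
- Label the suppression model exploratory if the restated power does not reach 80%.

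The cost is a short simulation and wording changes in two places. The stated power may become less favourable. No participants, visits or analyses are added.
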